#### **4.1.6 Packaging, labelling, and re-supply**

The empagliflozin and matching placebo tablets will be packaged into wallets, each containing 91 tablets blister packaging. This is sufficient for 12 weeks of treatment (84 tablets) and one week of reserve (7 tablets). For further details of packaging and the description of the label, refer to the ISF.

The investigational products will be provided by BI or a designated Clinical Research Organisation (CRO). They will be packaged and labelled in accordance with the principles of Good Manufacturing Practice (GMP). Re-supply to the sites will be managed via an IRT system, which will also monitor expiry dates of supplies available at the sites.

#### **4.1.7 Storage conditions**

Drug supplies will be kept in their original packaging and in a secure limited access storage area according to the recommended storage conditions on the medication label. A temperature log must be maintained for documentation. If the storage conditions are found to be outside the specified range, the process outlined in the ISF should be followed.

#### **4.1.8 Drug accountability**

The investigator and/or pharmacist and/or investigational drug storage manager will receive the investigational drugs delivered by the sponsor or delegate when the following requirements are fulfilled:

- Approval of the clinical trial protocol by the IRB / ethics committee;
- Availability of a signed and dated clinical trial contract between the sponsor and the investigational site,
- Approval/notification of the regulatory authority, e.g. competent authority,
- Availability of the curriculum vitae of the Principal Investigator,
- Availability of a signed and dated clinical trial protocol,
- Availability of the proof of a medical license for the Principal Investigator

Investigational drugs are not allowed to be used outside the context of this protocol. They must not be forwarded to other investigators or clinics. Patients should be instructed to return unused investigational drug.

The investigator and/or pharmacist and/or investigational drug storage manager must maintain records of the product's delivery to the trial site, the inventory at the site, the use by each patient, and the return to the sponsor or warehouse/drug distribution centre or alternative disposal of unused products. If applicable, the sponsor or warehouse/drug distribution centre will maintain records of the disposal.

These records will include dates, quantities, batch / serial numbers, expiry ('use-by') dates, and the unique code numbers assigned to the investigational product and trial patients. The investigator / pharmacist / investigational drug storage manager will maintain records that document adequately that the patients were provided the doses specified by the clinical Trial protocol (CTP) and reconcile all investigational products received from the sponsor.

At the time of returning investigational product to the sponsor/CRO at the end of the trial, the investigator / pharmacist / investigational drug storage manager must verify that all unused or partially used drug supplies have been returned by the clinical trial patients and that no supplies will remain in the investigator's possession.

#### **4.2 OTHER TREATMENTS, EMERGENCY PROCEDURES, RESTRICTIONS**

##### **4.2.1 Other treatments and emergency procedures**

The use of medication for the treatment of HF will be at the discretion of the Investigator and should be in accordance with local/international guidelines.

All concomitant (additional) medications and other therapies should be recorded on the appropriate pages of the eCRF.

The dobutamine administered during the MRS will be commercial stock supplied by the investigator's institution. It will be considered an auxiliary medicinal product (AMP) and administered as described in [Section 5.2.4](#). AEs/SAEs related to dobutamine will be documented as described in [Section 5.3.5](#).

For diabetic patients, concomitant antidiabetic medications should be adjusted individually as clinically indicated by the patient's usual diabetes care provider. Restrictions of antidiabetic background therapy are described in [Section 4.2.2](#).

Patients without a diagnosis of DM experiencing repeated or severe symptoms such as nervousness, sweating, intense hunger, trembling, weakness and palpitations should contact the Investigator or other healthcare professional, as these symptoms might be suggestive of hypoglycaemia. In the case of hypoglycaemia, in patients with or without DM, that may put the patient at risk (e.g. repeated symptomatic hypoglycaemia or severe hypoglycaemia), appropriate care should be provided at the discretion of the Investigator.

Special attention must be paid to the prevention of ketoacidosis. All patients must be made aware of this risk and need to be instructed to contact the Investigator or other healthcare professional in case of symptoms of metabolic acidosis, ketoacidosis and DKA.

Cases of DKA have been reported in patients treated with empagliflozin, including fatal cases [[c01678844](#)]. In a number of reported cases, the presentation of the condition was atypical with only moderately increased blood glucose values; below 14 mmol/L (250 mg/dL).

The risk of DKA must be considered in the event of non-specific symptoms such as nausea, vomiting, anorexia, abdominal pain, excessive thirst, difficulty breathing, confusion, unusual fatigue or sleepiness.

Patients should be assessed and treated for ketoacidosis immediately according to local guidelines if these symptoms occur, regardless of blood glucose level. If ketoacidosis is suspected, the trial medication should be discontinued, the patient should be evaluated, and prompt treatment should be initiated.

Patients who may be at higher risk of ketoacidosis while taking empagliflozin in this trial include patients on a very low carbohydrate diet (as the combination may further increase ketone body production), patients with an acute illness, patients with a history of pancreatitis or pancreatic surgery, patients with a history of alcohol abuse and patients with severe dehydration. Empagliflozin should be used with caution in these patients. In patients requiring insulin, caution should be taken when the dose of insulin is reduced.

In clinical situations known to predispose to ketoacidosis (e.g. prolonged fasting due to acute illness or surgery), the Investigator should consider monitoring for ketoacidosis and temporarily discontinue the trial medication.

There are no trial specific emergency procedures to be followed.

#### 4.2.2 Restrictions

The use of any SGLT-2 inhibitors or combined SGLT-1 and 2 inhibitors except the blinded trial medication is prohibited during the course of the trial. This also includes the 7 day period between the EOT and the Follow Up Visit.

If any restricted treatment is given during the conduct of the trial, the trial medication must be permanently discontinued.

If the patient is in need of any additional treatment during this period, this may be given at the discretion of the Investigator. The patient can still remain on trial medication.

Women of childbearing potential must use two medically approved methods of birth control throughout the study, and for a period of at least 7 days after last study drug intake. They must use one barrier method, i.e. condom or occlusive cap with spermicide, or vasectomised partner, and one highly effective non-barrier method including oral, injected or implanted hormonal contraceptives, intrauterine device or system.

#### 4.3 TREATMENT COMPLIANCE

Patients are requested to bring all remaining trial medication including empty package material with them when attending visits. Based on tablet counts, treatment compliance will be calculated as shown in the formula below.

$$\text{Treatment compliance (\%)} = \frac{\text{Number of tablets actually taken} \times 100}{\text{Number of tablets which should have been taken}}$$

Compliance should be between 80% and 120%. If the number of doses taken is not between 80-120%, site staff will explain to the patient the importance of treatment compliance.

If the assessment of compliance at Visit 4 indicates a compliance of less than 80%, the investigator may decide to perform limited Visit 4 assessments (as defined in [Section 3.3.4.1](#)) as the patient will not be used for the primary analysis.

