#### 3.3.4.1 Withdrawal from trial treatment

An individual patient is to be withdrawn from trial treatment if:

- The patient wants to withdraw from trial treatment, without the need to justify the decision.
- The patient does not want to undergo the trial assessments at visit 4 required to assess the primary endpoint.
- The patient needs to take concomitant drugs that interfere with the investigational product or other trial medication (see [Section 4.2.2](#)).
- The patient becomes pregnant. Note that the patient must be followed until the end of the pregnancy (see [Section 5.3.5.2](#)).
- The patient can no longer be treated with trial medication for other medical reasons (such as surgery, AEs or other diseases).
- The patient has repeatedly shown to be non-compliant with important trial procedures and/or, in the opinion of both the investigator and sponsor representative, is not willing or able to stick to the trial requirements in the future.

In the event that a patient is withdrawn from trial treatment prior to Visit 4, the patient should be asked to return all remaining trial medication. If the patient’s agrees, the following EOT safety assessments will be conducted;

- Pregnancy test
- Safety laboratory tests
- Vital signs

In addition, if the patient agrees, the patient will have a follow-up visit 7-14 days after the last dose of trial medication.

For all patients the reason for withdrawal from trial treatment (e.g. AEs) must be recorded in the eCRF. These data will be included in the trial database and reported.

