### 7.3 PLANNED ANALYSES

Adherence to the protocol (such as inclusion/exclusion criteria, times of measurement, compliance with intake of trial medication, treatment dispensing errors, prohibited concomitant medication, completeness and consistency of data) will be checked. Important protocol violations (IPVs) will be identified no later than in the Blinded Report Planning Meeting and provided in the TSAP.

The following analysis sets will be defined for this trial:

- Randomised set (RS):  
This subject set includes all randomised patients, whether treated or not.
- Treated set (TS):

This patient set includes all subjects from the RS who were documented to have received one dose of study drug. This is the Intent to treat (ITT) population.

- Per-protocol set (PPS):  
This patient set includes all patients from the TS who provide evaluable data at baseline and on-treatment for the primary endpoint and are not affected by protocol violations relevant to the statistical evaluation of the primary endpoint.

Whether a primary endpoint data is evaluable or a protocol violation is relevant will be decided no later than at the final Blinded Report Planning Meeting (BRPM).

Relevant protocol violations may include:

- Use of prohibited medication
- Patient was non-compliant to study drug intake (e.g.: study drug compliance <80%)

For both efficacy and safety analyses, treatment will be evaluated as treated.

Baseline will be defined as the last available measurement before start of randomised trial medication.

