9.2 Appendix 2: Important Protocol Deviations (iPDs)

The IPDs listing below is taken from the Medical and Quality Review Plan document, Version 2.0, dated 27th February 2018, for Study 1245-0148. The listing is tentative and subject to a review before the data lock. The updated version of the IPDs listing in the Medical and Quality Review Plan document will be used for the statistical analyses and the CTR.

Category / Code	Description	Requirements	Excluded from
A	Entrance criteria not met		
A1	Target indication not met		
A1.06	No chronic HF NYHA class II-IV	Inclusion criterion #2 violated	<None or PPS>
A1.07	Conditions on ejection fraction (EF) violated	Inclusion criterion #7 for Cohort A, #10 for Cohort B violated	PPS
A1.08	Conditions on NT-proBNP violated	Inclusion criterion #8 for Cohort A, #11 for Cohort B violated	PPS
A1.09	Conditions on HF violated	Inclusion criterion #1 and #9 for Cohort A, or #1 and #12 for Cohort B violated	PPS
A2	Inclusion criteria not met		
A2.02	Age out of range	Inclusion criterion #4 violated	None
A2.08	Specific inclusion criterion for women of child-bearing potential violated	Inclusion criterion #5 violated	None
A3	Exclusion criteria not met		
A3.44	Patient with unstable conditions	Exclusion criteria #1, #2, #4, #7, #11, #14, #15, #16 or #20 violated	None
tba	All other in/exclusion criteria		Individual discussion
B	Informed consent		
B1	Informed consent not available/not done	Informed consent date missing or inclusion criterion #6 violated	PPS
B2	Informed consent too late	Informed consent date was after Visit 1	None
C	Trial medication and randomisation		
C1	Incorrect trial medication		

	C1.02	Incorrect trial medication taken	Medication from wrong treatment arm taken for more than 20% of the overall treatment duration Can only be finally judged after data base lock (DBL) since unblinding information is required.	None
C2		Randomisation not followed		
	C2.01	Treated without randomisation	Patient treated according to eCRF, but not randomised according to IVRS.	None
C3		Non-compliance		
	C3.01	Non-compliance with study drug intake	Overall study treatment compliance outside 80% and 120% (exclusive) or study treatment compliance below 80% Missing compliance will be considered iPD.	None
C4		Medication code broken		
	C4.01	Medication code broken at site without just cause	Medication code was broken for no valid reason. Final decision at the DBL meeting based on medical judgement.	None
D		Concomitant medication		

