	D1.02	Use of other investigational drug	Review of eCRF for prohibited medication. Final decision at the DBL meeting based on medical judgement.	None
	D2.01	Use of protocol defined prohibited medication during treatment period	Use of SGLT-2 or combined SGLT-1 and 2 – inhibitors after randomization until the follow-up visit.	None
E		Missing data		
	E1.05	No baseline resting ³¹ P MRS result	No valid baseline PCr/ATP ratio at resting and dobutamine stress.	PPS
	E1.06	No baseline stress ³¹ P MRS result	No valid baseline PCr/ATP ratio at dobutamine stress.	PPS
F		Other		
	F1.02	Other PD related to safety only	Manually detected, safety related protocol deviations Final decision at the DBL meeting based on medical judgement.	None
	F1.03	Other PD related to primary endpoint	Final decision at the DBL meeting based on medical judgement.	PPS

	F1.04	Other PD related to patient rights	Manually detected protocol deviations related to patient rights Final decision at the DBL meeting.	None
--	-------	------------------------------------	---	------

APPROVAL / SIGNATURE PAGE**Document Number: c32019191****Technical Version Number:1.0****Document Name: 8-01-tsap-core-v2-2020-03-12****Title: 8-01-tsap-core-v2-2020-03-12****Signatures (obtained electronically)**

Meaning of Signature	Signed by	Date Signed
-----------------------------	------------------	--------------------

Approval-Biostatistics

21 Apr 2020 14:15 CEST

(Continued) Signatures (obtained electronically)

Meaning of Signature	Signed by	Date Signed
-----------------------------	------------------	--------------------

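### Protocol 4.3 lets the week-12 31P-MRS be skipped when compliance is below 80%, on the strength of an exclusion that Protocol 7.3 and the SAP leave open

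*Protocol*

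**What the plan says.** **Protocol 4.3** sets a target compliance of 80% to 120% by tablet count. For a Visit 4 result below 80%, "the investigator may decide to perform limited Visit 4 assessments", as defined in Protocol 3.3.4.1, and the reason given is "as the patient will not be used for the primary analysis". That statement carries no condition.

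**Protocol 3.3.4.1** introduces its list with "the following EOT safety assessments will be conducted" and names a pregnancy test, safety laboratory tests and vital signs. CMR and 31P-MRS are not on it.

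**Protocol 7.3** is softer. Among violations that may be relevant it gives "Patient was non-compliant to study drug intake (e.g.: study drug compliance <80" per cent), and it leaves relevance to a decision no later than the final Blinded Report Planning Meeting.

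**SAP 3.1** also defers to that meeting and describes its list of criteria as suggestive.

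**SAP 9.2, code C3.01** covers "Overall study treatment compliance outside 80% and 120% (exclusive) or study treatment compliance below 80" per cent, and also missing compliance. Its exclusion column reads *None*. The appendix states its own status: "The IPDs listing below is taken from the Medical and Quality Review Plan document, Version 2.0, dated 27th February 2018", and "The updated version of the IPDs listing in the Medical and Quality Review Plan document will be used for the statistical analyses". A separate code, F1.03 ("Other PD related to primary endpoint"), does lead to exclusion from the per-protocol set (PPS).

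**Sensitivity analysis.** Protocol 7.3.1 plans a randomised-set analysis of the primary endpoint without condition. SAP 3.2 ties it to a substantial number of violations. SAP 2.1.3 drops patients lacking a baseline or week-12 value from the primary analysis and imputes nothing for primary analyses.

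**The concern.** The protocol gives up a primary-endpoint measurement because the patient is said to be excluded anyway. Elsewhere the plan treats that exclusion as undecided, and the one place that codes it says *None*. SAP 1.4, which lists changes to the planned analysis, does not mention a departure from Protocol 4.3.

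The blinded meeting can change a code, but it cannot recover a scan that was not done. The randomised-set analysis exists to test whether the PPS exclusions bias the primary result, and patients excluded for low compliance are among those it most needs. Compliance arises after randomisation and could differ by arm, so their absence is not safely ignorable.

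**Working it through.** **The plan's own figures.** Protocol 7.7 gives an effect of 0.30, SD 0.28, two-sided alpha 0.05 and 80% power. A two-sample t-test has power 77.9% at 14 per arm and 80.9% at 15 per arm, so 30 evaluable patients per cohort reproduces. With 30% drop-out, 30 / 0.70 = 42.9, so 43 randomised also reproduces. Nothing here disputes either figure.

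**Who is below 80%.** At one tablet a day with Visit 4 on day 80, 84 or 88, the thresholds are 0.80 × 80 = 64.0, 0.80 × 84 = 67.2 and 0.80 × 88 = 70.4 tablets. Below 80% therefore means at most 63, 67 or 70 tablets. Such a patient may have taken most of the study drug, so the week-12 value is informative.

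**What happens to such a patient under the visible text.** This assumes a valid baseline scan and no other relevant deviation.

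| C3.01 after the blinded meeting | Week-12 scan done | Week-12 scan omitted |
|---|---|---|
| Stays *None* | In PPS; in randomised-set analysis | Out of PPS (no week-12 value); no observed value for randomised-set analysis |
| Becomes *PPS* | Out of PPS; in randomised-set analysis | Out of PPS; no observed value for randomised-set analysis |

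In the first row, PPS membership turns on the investigator's choice at Visit 4. In the second row the primary analysis is consistent, but the randomised-set analysis sees only the low compliers who happened to be scanned.

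**Size, for illustration.** The documents give no rate of compliance below 80%, so the inputs are assumptions. Take an arm of 15 (half of the 30 in Protocol 7.7). Suppose m of the 15 are unscanned and their mean change would have differed by g from that of the scanned patients. The full-arm mean differs from the scanned-only mean by m × g / 15:

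| m | g = 0.15 | g = 0.30 |
|---|---|---|
| 1 | 0.01 | 0.02 |
| 2 | 0.02 | 0.04 |
| 3 | 0.03 | 0.06 |

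The standard error of the treatment difference at 15 + 15 is 0.28 × √(2/15) = 0.102. The range of shifts is therefore 0.01 / 0.102 = 0.10 to 0.06 / 0.102 = 0.59 standard errors, or 3% to 20% of the planned effect. The treatment difference moves by this amount only if the other arm is unaffected. If m × g is the same in both arms, the shifts cancel.

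**A parallel mismatch.** Protocol 7.3 also lists use of prohibited medication among violations that may be relevant. SAP code D2.01 covers it, and its exclusion column also reads *None*.

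**The case against.** The best defence is that C3.01 is not an operative rule. SAP 3.1 and 9.2 call the list provisional. It comes from a plan dated 27 February 2018, before the current protocol of 14 August 2018, and it is visibly unfinished: code A1.06 still offers both outcomes, and another row has its code to be assigned. Protocol 7.3 sends the decision to the same blinded meeting. On this view one firm sentence stands beside deferrals to a single decision before unblinding. That is right as far as it goes, and a reader who infers that the SAP has decided to keep low compliers in the primary analysis goes beyond the text. It does not answer the loss of the scan, which happens before the meeting.

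A reader might infer three other things that the documents do not support:

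- *That the choice to scan favours an arm.* The investigator is blinded. The route to bias is compliance differing by arm, not knowledge of treatment.
- *That the PPS and randomised-set results must then agree.* Patients excluded for other reasons (codes A1.07 to A1.09, E1.06) who have both resting scans stay in the randomised set, so the two analyses can still differ. The blind spot concerns only low compliers who were not scanned.
- *That power is necessarily lost.* Protocol 7.7 allows a cohort to grow, up to 60, to reach 30 evaluable patients. That increase is optional and tied to drop-out, but it prevents any firm claim about power.

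Two further points stand in part. SAP 5.1 tabulates the analysis sets by arm and SAP 6.1 tabulates missed doses, so only the cross-listing of low compliance against scan done is missing. The SAP's sensitivity-analysis text is redacted: the ANCOVA promised in SAP 1.4 is not in the visible sections. Imputation may therefore be planned there, but it would not supply an observed value.

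**Conclusion.** The concern holds in limited form. Protocol 4.3 permits the omission of a scheduled primary-endpoint measurement by assuming an exclusion that Protocol 7.3, SAP 3.1 and code C3.01 do not settle. However the meeting rules, an omitted scan leaves the randomised-set analysis unable to show the effect of compliance exclusions for those patients.

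Severity is modest. The number of patients is unknown and may be zero. The illustrative shift of 0.01 to 0.06 in one arm's mean rests on assumed values of m and g and on an arm of 15. The conclusion about the sensitivity analysis rests on the visible SAP text.

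**What to change.** 1. **Keep the scan.** For any patient still to reach Visit 4, remove from Protocol 4.3 the option to omit the already scheduled resting 31P-MRS on compliance grounds. The cost is a protocol amendment with ethics and authority approval (Protocol 8.1) and some scanner slots. The resting scan comes before dobutamine (Protocol 5.2.4). The SAP was signed on 21 April 2020 and the documents do not say whether anyone is still before Visit 4; if nobody is, this step is moot. Patients withdrawn before Visit 4 remain unscanned in any case.
2. **Reconcile the rules before lock and unblinding of each cohort.** Bring Protocol 4.3 and 7.3 into line with C3.01, and Protocol 7.3 with D2.01. Either set the code to match the protocol or declare the departure in SAP 1.4. C3.01 combines low, high and missing compliance, while the firm statement in Protocol 4.3 concerns only values below 80%, so matching it means splitting the code. The cost is a small SAP edit.
3. **Report the overlap.** Produce a blinded listing, by cohort, of how many patients were below 80% and how many of those had a week-12 resting scan. The cost is one listing. It shows at once whether the issue is empty.
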